12.5.2 Secondary Analyses

12.5.2.1 Biomarkers of Exposure

12.5.2.1.1 Exhaled CO

CO in exhaled breath (expressed as ppm), will be measured using the Micro+™ Smokerlyzer® or similar device, conducted on Day -3 to Day 5, Day 30 Visit, Day 60 Visit and Day 90 Visit.

Descriptive statistics summarized by arm will be produced separately for all timepoints for all visits applicable for exhaled CO. Exhaled CO will be summarized on the natural scale as detailed in Section 12.1.3 “**Descriptive Statistics**”. Distribution will be tested for normality and appropriate non-parametric methods will be used in case of non-normally distributed data as described in 12.1 **General Considerations**.

Actual values and changes from baseline in levels of exhaled CO will be listed and summarized (Table 15.2.4.2.X and Listing 15.3.3.1). In addition line graphs will be produced for arithmetic means (and 95% CI) per randomization arm over all timepoints (Figure 15.1.2.5).

An ANCOVA model on exhaled CO (Day 5 and Day 90 Visit) will be used with terms for the baseline value, sex, average cigarette consumption over the previous 6 weeks prior to Admission and arm. The LS means on Day 5 and Day 90 for each arm along with the difference (CHTP 1.2 - CC) and 95% confidence interval (CI) will be presented in the tables (Table 15.2.4.1).

The statistical model and SAS code for the analysis of exhaled CO on Day 5 and at Day 90 Visit and COHb at Day 90 Visit will be the same as described in Section 12.5.1.1 “**Primary endpoints**”; except that there will be no log transformation of the data and back-transformation of the LS Means estimates of the difference.

If applicable, the table with descriptive statistics will be repeated for the group of subjects who attempt to quit (see section “**10.7 Quitters Population**”)

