Subjects who do not complete the study after randomization will not be replaced.

Investigational Products; Dose; and Mode of Administration:

- Carbon Heated Tobacco Product 1.2 (CHTP 1.2). CHTP 1.2 will be provided by the Sponsor
- Subject's own preferred commercially available non-menthol single brand of CC

Duration of Study:

The entire study duration per subject will be 128 to 169 days, including a Screening Period of up to 42 days prior to Admission on Day -3, a 9-day confinement setting (Day -3 to Discharge on Day 6) followed by a 85-day ambulatory setting (from the Discharge on Day 6 to the Discharge at Visit 4), and a 28-day Safety Follow-up Period. The EOS of the entire study is the last individual EOS time point during the study.

Statistical Methods:

Analysis of BoExp will be conducted on the natural log scale. The Day 5- or Visit 4-BoExp levels will be analyzed by means of a generalized linear model using randomized arm as covariate adjusting for the following Baseline information: sex, average cigarette consumption over the previous 6 weeks prior to Admission (value at Admission for stratification), and Baseline value of the BoExp. Relative effects will be provided. Assumptions of the analysis of variance (ANOVA) model will be tested. Markedly non-log normally distributed BoExp data will be transformed or analyzed by appropriate non-parametric methods.

Unless stated otherwise, all statistical tests will be conducted using a one-sided test with 2.5% type I error probability, and all quoted confidence intervals (CIs) will be two-sided 95% CIs.

Sample Size:

The analysis set to analyze the primary endpoints will be the Per-Protocol (PP) population. It is assumed that a minimal number of subjects will be excluded from the PP set in confinement for both arms and CC in ambulatory, whereas at least 50% will remain in the PP set in ambulatory for CHTP 1.2, therefore a 2:1 randomization ratio was chosen. Using the below assumptions, a total of 120 subjects (~80 in the CHTP 1.2 arm, and ~40 in the CC arm) will be randomized.)

Confidentiality Statement

Data and information contained in this document are considered to constitute trade secrets and confidential commercial information, and the legal protections provided to such trade secrets and confidential information are hereby claimed under the provisions of applicable law. No part of this document may be publicly disclosed without the written consent of Philip Morris Products S.A.

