12.4.4 Confirmatory Analyses

The hypothesis to be tested for each of the BoExp of the primary and secondary objectives that the geometric mean level on Day 5 of the BoExp (MHBMA; 3-HPMA; S-PMA; COHb) and at Visit 4 of the BoExp total NNAL, respectively, for CHTP 1.2 is lower relative to CC.

Analysis of BoExp will be conducted on the natural log scale. In order to test the following hypothesis:

- Null hypothesis (H_0): $m_1 \geq m_2$
- Alternative hypothesis (H_1): $m_1 < m_2$

Where m_1 and m_2 are the geometric means of the BoExp levels on Day 5 and at Visit 4, respectively, for CHTP 1.2 and CC respectively.

The transformed data will be analyzed by means of a generalized linear model using product arm as covariate adjusting for the following Baseline information: gender, average cigarette consumption over the previous 6 weeks, and Baseline value of endpoint. Estimates of differences between groups will be back-transformed to provide relative effects.

Assumptions of the analysis of variance model will be tested. Markedly non-lognormally distributed BoExp data will be transformed or analyzed by appropriate non-parametric methods.

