5.2 Secondary Objectives and Endpoints

1. To evaluate self-reported nicotine/tobacco product use throughout the entire exposure period, including dual-use in an ambulatory setting in smokers switching from CC to CHTP 1.2 as compared to smokers continuing to use CC.

Endpoint (measured daily):

- Number of CC or CHTP 1.2 used daily as reported on the usage log during the confinement period, and self-reported number of any nicotine/tobacco product use on a daily basis as reported on the product use diary during the ambulatory period
2. To determine the reduction of various BoExp to HPHCs in smokers switching from CC to CHTP 1.2 as compared to smokers continuing to use CC for 5 days and for 90 days.

Endpoints (Day 5 to Day 90 Visit):

- BoExp to HPHCs in urine (expressed as quantity excreted or concentration adjusted for creatinine in 24-hour urine):
 - MHBMA (Day 90 Visit only)
 - 3-HPMA (Day 90 Visit only)
 - S-PMA (Day 90 Visit only)
 - Total NNAL (Day 5 only)

- BoExp to benzo(a)pyrene: 3-hydroxybenzo(a)pyrene (Day 5, Day 90 Visit)
 - BoExp to pyrene: total 1-hydroxypyrene (total 1-OHP) (Day 5, Day 90 Visit)
 - BoExp to N-nitrosornicotine: total N-nitrosornicotine (total NNN) (Day 5, Day 90 Visit)
 - BoExp to 4-aminobiphenyl: 4-aminobiphenyl (4-ABP) (Day 5, Day 90 Visit)
 - BoExp to 1-aminonaphthalene: 1-aminonaphthalene (1-NA) (Day 5, Day 90 Visit)
 - BoExp to 2-aminonaphthalene: 2-aminonaphthalene (2-NA) (Day 5, Day 90 Visit)
 - BoExp to o-toluidine: o-toluidine (o-tol) (Day 5, Day 90 Visit)
 - BoExp to acrylonitrile: 2-cyanoethylmercapturic acid (CEMA) (Day 5, Day 90 Visit)
 - BoExp to ethylene oxide: 2-hydroxyethylmercapturic acid (HEMA) (Day 5, Day 90 Visit)
 - BoExp to crotonaldehyde: 3-hydroxy-1-methylpropyl-mercapturic acid (3-HMPMA) (Day 5, Day 90 Visit)
 - BoExp to CO:
 - CO in exhaled breath (expressed as ppm) (Day 5, Day 90 Visit)
 - COHb in blood (expressed as % of saturation of hemoglobin) (Day 90 Visit only)
3. To describe the levels of BoExp over the entire exposure period in smokers switching from CC to CHTP 1.2 as compared to smokers continuing to use CC.
- Endpoints (Day 1 to Day 90 Visit):
- BoExp to CO:
 - CO in exhaled breath (expressed as ppm)
 - COHb in blood (expressed as % of saturation of hemoglobin)
 - BoExp to HPHCs in urine (expressed as quantity excreted and concentration adjusted for creatinine in 24-hour urine):
 - MHBMA
 - 3-HPMA
 - S-PMA
 - Total NNAL
 - Total 1-OHP
 - Total NNN
 - 4-ABP
 - 1-NA
 - 2-NA
 - o-tol

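### COHb at the Day 90 Visit is modelled untransformed, against the log scale in the protocol, the SAP's Day 5 COHb model and the other primary biomarkers, and SAP Section 9 does not record it

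*SAP*

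**What the plan says.** The sentence at issue is in SAP 12.5.2.1.1, under the heading Exhaled CO. It says the model and code for "exhaled CO on Day 5 and at Day 90 Visit and COHb at Day 90 Visit will be the same" as for the primary endpoints, "except that there will be no log transformation of the data and back-transformation of the LS Means estimates of the difference". No other place in the SAP gives a model for COHb at the Day 90 Visit.

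The protocol synopsis (Statistical Methods) says "Analysis of BoExp will be conducted on the natural log scale. The Day 5- or Visit 4-BoExp levels will be analyzed" by a linear model with baseline adjustment, and "Relative effects will be provided". Protocol 12.4.4 opens with "The hypothesis to be tested for each of the BoExp of the primary and secondary objectives", again puts the analysis on the log scale, and adds "Estimates of differences between groups will be back-transformed to provide relative effects".

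SAP 12.5.1.1 summarises COHb on the log scale, fits a log-transformed ANCOVA to COHb on Day 5, and plots COHb geometric means over all timepoints. It also logs total NNAL at the Day 90 Visit. SAP 12.5.2.1.2 logs MHBMA, 3-HPMA and S-PMA at the Day 90 Visit and total NNAL on Day 5, each reported as a percent reduction.

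**The concern.** COHb is the only one of the five primary biomarkers whose modelled scale changes between visits, and no reason is given. Secondary objective 2 in SAP 5.2 reads "To determine the reduction of various BoExp to HPHCs in smokers switching from CC to CHTP 1.2" at 5 and 90 days, and it lists COHb at the Day 90 Visit among its endpoints. With the untransformed model, the planned inference for that endpoint is an absolute difference, so the reduction the objective asks for has no model-based estimate with an interval.

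There is also a risk of misreading. Judging by its title, Table 15.2.4.1 covers biomarkers for both primary and secondary objectives. A Day 5 COHb percent reduction could then stand beside a Day 90 COHb difference whose unit is also percent, meaning percent saturation.

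The protocol allows another approach only for markedly non-lognormal data. Here the natural scale is fixed in advance with no such reason, and it is missing from the SAP's own list of departures.

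**Working it through.** **1. Scale by place**

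| Place | COHb Day 5 | COHb Day 90 | Other four primary biomarkers |
|---|---|---|---|
| Protocol synopsis | log, relative effect | log, relative effect | log, relative effect |
| SAP summaries and figure (12.5.1.1) | log, geometric means | log, geometric means | log, geometric means |
| SAP model (12.5.1.1, 12.5.2.1.1, 12.5.2.1.2) | log, % reduction | untransformed, difference | log, % reduction, both visits |

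The seven items in SAP Section 9 concern the QSU-brief and mCEQ models, descriptive statistics by stratum, demographics on the FAS, SES categories, the laboratory tabulation, the 8-epi-PGF2α ratio and the Quitters population. None concerns scale.

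**2. The plan's own COHb figure.** SAP Section 8 gives a ratio of 0.40, CV 0.32, 80:40 subjects, one-sided 2.5%, a 50% reduction threshold, and test-wise power of 96% on Day 5.

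- Log SD = √ln(1 + 0.32²) = 0.3122
- Distance to threshold = ln(0.50/0.40) = 0.2231
- SE = 0.3122 × √(1/80 + 1/40) = 0.0605
- Power = Φ(0.2231/0.0605 − 1.96) = 95.8%

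The stated 96% is reproduced by a log-scale ratio calculation, so the plan treated COHb as lognormal at the design stage.

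**3. What each model would report at Day 90.** Assumption: the Day 5 ratio and CV carry over, with no covariate adjustment. I use 40:40, since Section 8 assumes that at least 50% of the 80 CHTP 1.2 subjects stay per-protocol in the ambulatory period.

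Log scale:
- SE = 0.3122 × √(1/40 + 1/40) = 0.0698
- 95% CI for the ratio = 0.348 to 0.460
- Reduction 60%, 95% CI 54.0% to 65.2%
- With all 80 retained (80:40): 54.9% to 64.5%

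Untransformed scale, with SD = 0.32 × mean in each arm. The documents give no cigarette-arm COHb mean, so the means below are assumptions:

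| Assumed CC mean (% saturation) | Difference | SE | 95% CI |
|---|---|---|---|
| 4 | −2.4 | 0.218 | −2.83 to −1.97 |
| 5 | −3.0 | 0.272 | −3.54 to −2.46 |
| 6 | −3.6 | 0.327 | −4.25 to −2.95 |

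All three rows are the same 60% reduction, and none has an interval on the percent scale.

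**4. Interval validity.** With equal CVs, the untransformed SD in the CC arm is 1/0.40 = 2.5 times that in the CHTP 1.2 arm, while the model pools the variance. At 40:40 this does no harm. At 80:40 with a CC mean of 5, the pooled SE is 0.205 against a true SE of 0.263. Simulated coverage of the nominal 95% interval is then about 87% (about 90% at 60:40, about 95% at 40:40). The log model holds 95% in all three cases.

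**The case against.** The strongest counter-arguments are these.

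- **Reach of the protocol.** Protocol 12.4.4 sits under the primary endpoints and, after its broad opening, names only the five primary biomarkers at their primary visits. Protocol 12.5 describes secondary endpoints only descriptively. This stands: the log-scale rule for Visit 4 COHb rests mainly on the synopsis. The synopsis is explicit, though, and the conflict inside the SAP does not depend on the protocol.
- **Distribution check.** SAP 12.1 says markedly non-normal data will be transformed or analysed non-parametrically, which could bring COHb back to the log scale. It could, but only after looking at the data, and a moderate skew might not trigger it.
- **Readability.** SAP 12.1 shows the LS mean for each arm beside the difference, so a point percent reduction can be read off. Day 90 geometric means with intervals and percent changes are also planned. This is correct. What is missing is the adjusted percent reduction with its interval.
- **Sampling time.** COHb is drawn around 8 PM on Day 5 but at any time during the Day 90 Visit (SAP 11.3). This weakens the carry-over of Day 5 values used above and limits comparison across visits on any scale. It is not a reason to change scale.
- **Documentation only, or a drafting slip.** The clause sits in an exhaled CO paragraph and may be unintended, and the protocol leaves detail to the SAP. Even so, a programmer would implement it as written.

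**Conclusion.** The concern holds. As written, the Day 90 COHb model contradicts the protocol synopsis, the SAP's own treatment of COHb, and its treatment of the other primary biomarkers, with no stated reason and no Section 9 entry.

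The consequence is minor. One secondary endpoint loses its model-based percent reduction and interval. The Day 5 confirmatory COHb test, the alpha, the sample size and the direction of any conclusion are untouched. The size in step 3 assumes that the Day 5 ratio and CV hold at Day 90. The undercoverage in step 4 needs that assumption too, and it arises only if clearly more than half of the CHTP 1.2 arm stays per-protocol.

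Exhaled CO is also placed on the natural scale without a Section 9 entry, but its summary, figure and model agree with one another, so that is a documentation matter and not part of this finding.

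**What to change.** In SAP 12.5.2.1.1, remove Day 90 COHb from the sentence that drops the log transformation. Add one sentence saying that COHb at the Day 90 Visit is analysed with the log-scale ANCOVA of 12.5.1.1, with geometric LS means and percent reduction with 95% CI reported in Table 15.2.4.1.

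The cost is one or two sentences. The code already exists for Day 5, no new data or tables are needed, and no power figure changes. It should be done before database lock, so that the scale is not chosen after the data are seen. If the sponsor does want the untransformed difference, Section 9 should list it with a reason.

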12.5.2.1.2 Urinary Biomarkers of Exposure

The Urinary Biomarkers of Exposure assessed as secondary endpoints are total 1-OHP, Total NNN, 4-ABP, 1-NA, 2-NA, o-tol, CEMA, HEMA, Total 3-OH-B[a]P, HMPMA assessed at Day 5 and Day 90 Visit, MHBMA, 3-HPMA and S-PMA assessed at Day 90 Visit and Total NNAL assessed at Day 5.

The urine parameters will be expressed as concentrations adjusted for creatinine. In addition, the quantity excreted over 24 hours for all Biomarkers of Exposure will be presented. These endpoints will be log-transformed.

The values and percent changes for urinary BoExp in the quantity excreted over 24-hours and the concentration adjusted for creatinine will be listed and summarized (Table 15.2.4.3-12.1 and 15.2.4.3-12.2 and Listing 15.3.3.1). In addition line graphs will be produced for arm geometric means (and 95% CI) over all timepoints (Figure 15.1.2.1-25).

The analysis will compare the log-transformed urinary concentrations adjusted for creatinine and the quantity excreted over 24-hours between the CHTP 1.2 and CC arms on Day 5 and Day 90 Visit for 1-OHP, total NNN, 4-ABP, 1-NA, 2-NA, o-tol, CEMA, HEMA, Total 3-OH-B[a]P, HMPMA.

The analysis will also compare the log-transformed urinary concentrations adjusted for creatinine and the quantity excreted over 24-hours between the CHTP 1.2 and CC arms for MHBMA, 3-HPMA, S-PMA at Day 90 Visit and for total NNAL at Day 5 as well as the quantity excreted over 24-hours between the arms for MHBMA, 3-HPMA and S-PMA at Day 5 and for total NNAL at Day 90 Visit.

The statistical model and SAS code will be the same as described in Section 12.5.1.1 “**Primary endpoints**”. Note that for the analyses at Day 90 Visit, the p-value will only be shown if the one-sided p-value at Day 5 was significant (i.e. < 0.025). The geometric LS means for each arm along with the reduction (i.e: 100% - ratio of CHTP 1.2 : CC (%)) and 95% CI will be presented in the tables (Table 15.2.3.2, Table 15.2.4.1)

The least squares (LS) means and estimate of the difference along with its 95% CI will be back-transformed before presenting in the tables. The geometric LS means for each arm along with the reduction (i.e: 100% - ratio of CHTP 1.2 : CC (%)) and 95% CI will be presented in the tables (Table 15.2.4.1).

12.5.2.1.3 NEQ

NEQ will be expressed as concentrations adjusted for creatinine and as the quantity excreted over 24 hours. It will be assumed that NEQ is log-normally distributed.

The values and percent changes for NEQ in the quantity excreted over 24-hours and the concentration adjusted for creatinine will be listed and summarized (Table 15.2.4.13.X and Listing 15.3.3.1). In addition line graphs will be produced for arm geometric means (and 95% CI) over all timepoints (Figure 15.1.2.26 and 15.1.2.27).

The analysis will compare the log-transformed NEQ between the CHTP 1.2 and CC arms on Day 5 and Day 90 Visit. The statistical model and SAS code will be the same as described in Section 12.5.1.1 “Primary endpoints” (Table 15.2.4.1).

In addition, a repeated measures mixed model on the log-transformed NEQ will be used with terms for log-transformed baseline, sex, average daily CC consumption over the last 6 weeks as reported during admission, arm, timepoint, and the interaction between arm and timepoint. The interaction term will be removed if $p > 0.1$.

The SAS code to be used is shown below:

```
Proc mixed data=_data_ method=REML;
Class arm sex cigarette_cons time_point_cat subject period;
Model log(NEQ) = log(base) sex period cigarette_cons arm
arm*time_point time_point;
Repeated time_point_cat / subject=subject type=un;
Lsmean arm / diff alpha=0.05 cl;
Run;
```

The least squares (LS) means and estimate of the difference along with its 95% CI will be back-transformed before presenting in the tables. The geometric LS means for each arm along with the reduction (i.e: 100% - ratio of CHTP 1.2 : CC (%)) and 95% CI will be presented in Table 15.2.4.14. This will be done for all individual timepoints. If the interaction term is present in the model, the reduction will also be shown for the individual timepoints.

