9 CHANGES FROM THE PROTOCOL SPECIFIED STATISTICAL ANALYSIS

- Statistical analysis for the QSU-brief questionnaire data and the mCEQ questionnaire data will be performed including interaction terms for arm and time point to enable least square means to be calculated at each time point in order to explore the pattern of the CHTP 1.2 effect over time. The main comparison between arms will be the comparison over all of the time points.

Reason for change:

This analysis would capture the evolution of perception of the product and the adaptation process taking into account the subjects' repeated measurements.

- The descriptive statistics of the biomarkers of the primary endpoints will also be calculated per stratification factor.

Reason for change:

The protocol specified that primary endpoint analyses would be done by stratification factor, and this clarifies that descriptive statistics will also be presented by stratification factor.

- The summary of demographics will also be performed on the FAS.

Reason for change:

If the safety population differs from the FAS, then a summary of the demographics for the FAS is also required.

- The categorisation of the SES questionnaire into low, moderate and high SES will not be performed.

Reason for change:

There is no scoring algorithm available for the Socio-Economic Status questionnaire in the study population.

- The number and percentage of subjects with clinical findings will not be tabulated by sequence for laboratory parameters.

Reason for change:

No sequence occurred in this study. The tabulation will be done by arm. The error is corrected in this Analysis Plan.

- The endpoint "Ratio of 8-epi-prostaglandin F2 α (8-epi-PGF2 α) to prostaglandin F2 α (PGF2 α)" will only be listed.

Reason for change:

During the course of the study, the most recent development of the assay to measure the 8-epi-PGF2 α to PGF2 α ratio showed that the ratio is not an effective endpoint for the

determination of oxidative stress. The collection of samples and the analysis for this endpoint was stopped and the results will only be listed in the Clinical Study Report.

- The definition of the Quitters population was added in section **10.7 Quitters Population**.

Reason for change:

The purpose of this addition was to clarify the population on which exploratory endpoint 4 will be assessed.

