12.5.2.2 Nicotine and Cotinine Concentrations

It is assumed that Nicotine and Cotinine concentrations are log-normally distributed.

The descriptive analysis will be the same as described in Section 12.5.1.1 “Primary endpoints”.

The percent change from baseline will be calculated. The concentrations of nicotine and cotinine will be listed and summarized along with this change (Table 15.2.4.15 and Listing 15.3.4.1). Line graphs of the nicotine and cotinine concentration profiles across all study days showing geometric mean and 95% CI will also be produced (Figure 15.1.2.28).

Nicotine and cotinine values will also be analyzed in a repeated measures mixed model on the log-transformed values, as described in section “12.5.2.1.3 NEQ” (Table 15.2.4.16).

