12.5.3.1.1 Urge-to-Smoke Questionnaire of Smoking Urges Brief

All summaries, profiles and analysis will be presented for the CHTP 1.2 and CC arms.

The change from baseline will be calculated for the total score and the two domain scores (relief and reward). The total score and two domain scores, along with the change from baseline will be summarized (Table 15.2.5.1). The answers to the individual questions, along with the domain scores, total scores and changes from baseline will be listed (Listing 15.3.5.1).

The profiles of the arithmetic means and LS Mean differences per timepoint for the total score and two domain scores will be produced (Figure 15.1.3.1 and Figure 15.1.3.2).

The analysis will compare each post baseline timepoint in the domain and total scores. A repeated measures mixed model will be used with terms for baseline QSU-BRIEF score, sex, average daily CC consumption over the last 6 weeks as reported during admission, arm, timepoint, and the interaction between arm and timepoint. The interaction term will be removed if $p > 0.1$.

The SAS code will be the same as the repeated measures model described in Section “12.5.1.1 Primary endpoints”.

LS means for each arm along with the difference (CHTP 1.2 - CC) with 95% CI will be presented in table 15.2.5.2.

All figures, summaries and analyses will be performed on the Per Protocol Populations.

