15.1.2.46	Urinary 11-DTX-B2 Quantity Excreted over 24 hours Geometric Mean and 95% CI – Per Protocol Population
15.1.2.47	8-epi-PGF2 α Geometric Mean and 95% CI – Per Protocol Population
15.1.2.48	8-OHdG Geometric Mean and 95% CI – Per Protocol Population
15.1.2.49	TAC Geometric Mean and 95% CI – Per Protocol Population
15.1.3.1	Questionnaire of Smoking Urges-brief Total Score and Factor Scores Arithmetic Mean and 95% CI – Per Protocol Population
15.1.3.2	Questionnaire of Smoking Urges-brief Total Score and Factor Scores Arithmetic Least Squares Mean Differences and 95% CI – Per Protocol Population
15.1.3.3	Modified Cigarette Evaluation Questionnaire Subscales Arithmetic Mean and 95% CI – Per Protocol Population
15.1.3.4	Modified Cigarette Evaluation Questionnaire Subscales Arithmetic Least Squares Mean Differences and 95% CI – Per Protocol Population

Tables	Title
15.2.1.1	Summary of Subject Disposition – All Screened Subjects
15.2.1.2.1	Summary of Reasons for Screen Failure – All Screened Subjects
15.2.1.2.2	Summary of Reasons for Discontinuations – All Enrolled Subjects
15.2.1.3.1	Summary of Protocol Deviations – Safety Population
15.2.1.3.2	Analysis Sets and Reasons for Exclusions – All Screened Subjects
15.2.1.4.1	Summary of Demographics and Other Baseline Characteristics – Safety Population
15.2.1.4.2	Summary of Demographics and Other Baseline Characteristics – FAS
15.2.1.4.2.1	Summary of Demographics and Other Baseline Characteristics by Sex – FAS
15.2.1.4.2.2	Summary of Demographics and Other Baseline Characteristics by Cigarette Consumption – FAS
15.2.1.4.2.3	Summary of Demographics and Other Baseline Characteristics by Product Use Category – FAS
15.2.1.4.3	Summary of Demographics and Other Baseline Characteristics – Per Protocol Population
15.2.1.4.3.1	Summary of Demographics and Other Baseline Characteristics by Sex – Per Protocol Population
15.2.1.4.3.2	Summary of Demographics and Other Baseline Characteristics by Cigarette Consumption – Per Protocol Population
15.2.1.4.3.3	Summary of Demographics and Other Baseline Characteristics by Product Use Category – Per Protocol Population
15.2.1.5	Summary of Current Cigarette Brands – FAS
15.2.1.6	Summary of Medical History – Safety Population
15.2.1.7	Summary of Concomitant Diseases – Safety Population
15.2.2.1.1	Descriptive Statistics of Use of CHTP 1.2 Product and CC during Confinement – Safety Population

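### For QSU-brief and mCEQ, removing the arm-by-timepoint interaction when p > 0.1 undoes the timepoint-specific arm differences that SAP Sections 9 and 12.5.3.1 promise

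*SAP*

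**What the plan says.** **Purpose of the term.** SAP Section 9 opens its list of changes with these two questionnaires: "Statistical analysis for the QSU-brief questionnaire data and the mCEQ questionnaire data will be performed" with the interaction added "to enable least square means to be calculated at each time point". The stated aim is to explore how the product effect evolves. The same item names the comparison over all timepoints as the main one.

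**Promised outputs.** For QSU-brief, Section 12.5.3.1.1 states: "The analysis will compare each post baseline timepoint in the domain and total scores". It also plans, without condition, profiles of LS mean differences by timepoint. Section 12.5.3.1.2 promises the same timepoint comparison for the mCEQ subscales. In Section 13.3.1, Figure 15.1.3.2 is titled "Questionnaire of Smoking Urges-brief Total Score and Factor Scores Arithmetic Least Squares Mean Differences and 95% CI", and Figure 15.1.3.4 is the mCEQ counterpart.

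**The rule.** Both sections then repeat the sentence that appears in Section 12.5.2.1.3 (NEQ): "The interaction term will be removed if $p > 0.1". Neither says what replaces the timepoint comparison if the term goes.

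**NEQ, nicotine and cotinine.** Section 12.5.2.1.3 shows the reduction by timepoint if the interaction is in the model, and separately compares the arms by ANCOVA on Day 5 and at the Day 90 Visit. Section 12.5.2.2 says: "Nicotine and cotinine values will also be analyzed in a repeated measures mixed model on the log-transformed values", following the NEQ model. It plans no separate Day 5 or Day 90 ANCOVA.

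**The concern.** Without the interaction, the model contains arm and timepoint as additive effects. The difference between arms is then a single number by construction. A figure of differences by timepoint can still be drawn, but it is a flat line that carries no information about time, which is what Section 9 wanted the term for.

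The term is kept or dropped by a test on the same data. With eight timepoints and two arms that test has 7 degrees of freedom, and it can easily miss a modest early difference that fades as users adapt. If it does miss, the early difference is reported as an average across all visits. The interval around that average is computed as if the additive model had been fixed in advance.

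**Working it through.** **The passages side by side (QSU-brief, mCEQ)**

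| SAP place | What it needs or does |
|---|---|
| Section 9 | Interaction in the model, to give LS means by timepoint and show the pattern over time |
| 12.5.3.1.1, 12.5.3.1.2 | Arm comparison at each post-baseline timepoint |
| 13.3.1, Figures 15.1.3.2 and 15.1.3.4 | LS mean differences with 95% CI |
| 12.5.3.1.1, 12.5.3.1.2 | Interaction deleted if p > 0.1 |

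The first three need differences that may vary by timepoint. The fourth removes them whenever the pre-test is not significant. If there is no true interaction, that happens in 90% of trials, since the test has level 0.10.

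**How often the term survives.** The documents give no power figure for this model and neither the within-subject correlation nor an effect profile, so the following is an illustration.

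Inputs from the documents: eight post-baseline assessments (Days 1 to 5, then Days 30, 60 and 90; SAP 7.4.3 and 7.4.4); 80 and 40 subjects (SAP Section 8); test level 0.10.

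Assumed: compound symmetry with correlation ρ of 0.3 to 0.7; timepoint categorical; an arm difference falling in equal steps over Days 1 to 5 to zero from Day 30, that is (0.5, 0.4, 0.3, 0.2, 0.1, 0, 0, 0) SD, rescaled to start at 0.25, 0.30 or 0.50 SD.

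Formula: the Wald statistic is noncentral chi-square with 7 df and
ncp = Σ(dᵢ − d̄)² / [(1 − ρ)(1/80 + 1/40)].
The term is kept if the statistic exceeds 12.02.

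Example, 0.25 SD and ρ = 0.5: d̄ = 0.75/8 = 0.094. Σ(dᵢ − d̄)² = 0.1375 − 8 × 0.09375² = 0.0672. ncp = 0.0672/(0.5 × 0.0375) = 3.58. P(kept) = 34%.

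| Day 1 difference | ρ = 0.3 | ρ = 0.5 | ρ = 0.7 | Equal-weight average if dropped |
|---|---|---|---|---|
| 0.25 SD | 27% | 34% | 50% | 0.09 SD |
| 0.30 SD | 35% | 45% | 66% | 0.11 SD |
| 0.50 SD | 74% | 88% | 98% | 0.19 SD |

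**Effect on an interval.** A second assumed pattern has an arm difference that changes once, between confinement and the ambulatory visits. It takes ρ of 0.3 to 0.7 and either 80 v 40 or, for the 50% ambulatory per-protocol retention assumed in SAP Section 8, 40 v 40 at the ambulatory visits. The Day 90 difference is read from whichever model the pre-test leaves (40,000 simulated trials per setting, covariance treated as known).

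| True change | Term dropped | Coverage of nominal 95% CI at Day 90 |
|---|---|---|
| 0.2 SD | 45% to 76% | 82% to 92% |
| 0.3 SD | 11% to 56% | 74% to 94% |
| 0.5 SD | 0% to 14% | 85% to 95% |

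**The shared code.** The program in 12.5.2.1.3 has time_point_cat in CLASS but time_point in MODEL, and requests LS means for arm only. A numeric variable absent from CLASS is fitted as a linear trend. As written, the code gives no arm difference by timepoint even when the interaction stays. Section 12.5.3.1.1 also points to a repeated-measures model in 12.5.1.1, which contains only an ANCOVA.

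**The case against.** Much can be said for the plan.

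- **The rule is pre-specified.** Rule and threshold are fixed in the SAP before database lock, so no analyst discretion enters. That stands, but the model is still selected on the data and the intervals take no account of it.
- **The named main comparison survives.** Section 9 makes it the one over all timepoints, which needs no interaction. That stands.
- **Time patterns remain visible.** Descriptive summaries and profiles by arm and timepoint are planned. That stands, though for the questionnaires they are not the model-based differences promised.
- **Large variation is mostly kept.** At 0.5 SD on Day 1 the term stays in 74% to 98% of the illustrated trials. That stands; the weakness lies with modest effects.

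A reader might infer that the conflict with Section 9 extends to NEQ, nicotine and cotinine. It does not. Section 9 names only the two questionnaires, and 12.5.2.1.3 openly makes the NEQ reduction by timepoint conditional.

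A reader might also infer that dropping the term removes every estimate by timepoint. It does not. With timepoint still in the model, each arm's LS mean at each timepoint can be estimated; only the difference between arms becomes constant.

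**Conclusion.** For QSU-brief and mCEQ the SAP contradicts itself: it promises arm differences at each timepoint and then deletes the term that lets them differ. What is lost is those differences and valid intervals after the pre-test. The pooled comparison and each arm's LS means by timepoint remain.

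For NEQ, nicotine and cotinine only the pre-test concern applies. It matters least for NEQ, which keeps its Day 5 and Day 90 ANCOVAs, and most for nicotine and cotinine, which have none.

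The primary endpoints are unaffected, because their ANCOVA contains no such term. The point is minor in consequence, being confined to secondary and exploratory analyses.

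The retention and coverage figures rest on assumed correlations, effect profiles and a categorical time effect. They show the direction and plausible range and are not predictions for this trial. The contradiction does not depend on them.

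**What to change.** 1. Delete the p > 0.1 rule in 12.5.3.1.1 and 12.5.3.1.2, and in 12.5.2.1.3 for consistency, which also covers nicotine and cotinine.
2. Keep arm, timepoint and arm-by-timepoint in the model in all cases.
3. Report the arm difference with 95% CI at each timepoint, with the average over timepoints as the main comparison already named in Section 9. Give the interaction p-value descriptively.
4. In the shared code, use the same categorical time variable in CLASS and MODEL, and request LS means and differences for arm by timepoint. Deleting the rule alone would not produce the planned figures.
5. Point 12.5.3.1.1 to the repeated-measures model in 12.5.2.1.3 instead of 12.5.1.1.

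The cost is a few lines of SAP wording and code and a few degrees of freedom. No new data are needed, and no stated power figure changes.
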